The "Sleep Revolution" is a major, Pan-European research project financed by the European Union Horizon 2020 program. The SR aims to tackle the above-mentioned major shortcomings by developing machine learning tools to individualize OSA care and to identify the wide range of OSA phenotypes better in the diagnostic process. This allows for more personalized treatment options, including increased patient participation. The project aims to design a digital platform that functions as a bridge between researchers, patients, and clinicians, with an electronic sleep diary, objective cognitive tests, and questionnaires in a mobile application. The SR aims to create new pathways for improved clinical practice in sleep medicine, in particular for sleep apnea management.

In this context, the current study is designed on a work package within the project, the new SR pathway for sleep apnea diagnosis and treatment follow up needs to be validated and tested with regard to the feasibility of new technologies including and data analysis approaches:

- Self-applied polysomnography
- Diagnostic assessment over long time periods including 3 consecutive nights of advanced sleep testing, at least one week of testing with actigraphy, physical activity, sleep symptom questionnaire, and sleep diary
- Artificial Intelligence based analysis of sleep tests for characterization of sleep, respiratory events and cardiovascular function with quality control by healthcare professionals (semi-automated process)
- Digital platform for data transfer from the patient to the health care professional
- Validation of new sleep parameters like hypoxic burden, sleep disturbance index and pulse wave derived cardiovascular indices against comorbidities, baseline symptoms, and response to treatment
- The recently developed European Sleep Questionnaire (ESQ)

The current statistical analysis plan is focussed on the predefined primary and main secondary objectives of the study (protocol version 1.3 from May 29 2023). Evaluation of all different

components of the study data will require several years of additional research and will not be captured in this document.

Study Objective:

- Primary objective: To compare staff time spent to complete the sleep apnea diagnostic pathways between standard care and the Sleep Revolution management model intended for patients with suspected obstructive sleep apnea (OSA).
- Secondary objective: To evaluate novel Sleep Revolution diagnostic variables and their relation to symptom burden, patient 's help request during baseline assessment and outcome of sleep apnea treatment with CPAP after 3 months.
- Further secondary objectives: Feasibility and safety of the self-applied sleep testing and the digital platform for both sleep and symptom assessment

Study Design:

The study is performed at 24 sites of the European Sleep Apnea Database (ESADA) network in 15 European countries. Most relevant details of the study design are listed below:

- Study SR-001 is a multi-center, 2-arm, cross-over study comparing the diagnostic impact and accuracy of two different diagnostic pathways on the outcome of diagnosis and CPAP treatment in patients with suspected OSA. Patients referred to one of 24 sleep centers of the ESADA network participating in the Sleep Revolution project will be studied using both the clinical routine of OSA evaluation (standard care) and the novel Sleep Revolution based diagnostic pathway including self-applied polysomnography over three nights, digitally based symptom evaluation, and actigraphy based assessment of sleep wake rhythm and physical activity (experimental condition). Study participants will be randomized with respect to the order of two diagnostic pathways. The decision on diagnosis and treatment will be based on information from the first diagnostic procedure (SC or SR), the results from the second pathway will be blinded both to the investigator (sleep specialist) and the patient.
- Following diagnostic steps including sleep testing, symptom assessment and evaluation of physical status evaluation, patients will receive information regarding the sleep disorder diagnosis by the sleep specialist. In case of a diagnosis of clinically relevant OSA, treatment recommendations will be provided. Only patients initiating therapy with PAP will be approached for participation in the subsequent part of the study- treatment start and follow up for 3 months.
- Information from sleep related examinations in the standard pathway will be manually scored by skilled technicians at each center using predefined criteria. Sleep tests in the SR pathway will be pre-scored by artificial intelligence-based algorithms for characterization of sleep and respiration, and the three PSG in the SR pathway will be manually edited only in epochs identified as unclear by the automated scoring process. For patients with indication for PAP, the titration, training and support will be organized applying local routines at each study center. At PAP-follow up, one night sleep evaluation using the SR self-applied polysomnography procedure will be performed in all patients.

- Evaluation of symptoms and cognitive function with standard care questionnaires and the new European Sleep Questionnaire will be performed together with physical activity assessment at baseline, during treatment and at 3 months follow up.
- Estimated number of patients per center to be randomized: N=42 is the targeted number per site

Study Population:

- Main Inclusion Criteria:
 - Referral to the sleep center due to suspected obstructive sleep apnea as the main question for evaluation
 - Male or female aged 18 years and above
 - \circ $\;$ Willing and able to provide written informed consent $\;$
 - Willing and able to comply with the study design schedule and other requirements
 - (e.g. no long-term travel conflicting with the planned visits throughout the study)
- Main exclusion criteria:
 - o Any ongoing treatment for OSA or Central Sleep Apnea
 - Known significant hypercapnic respiratory failure due to chronic obstructive pulmonary disease or other respiratory condition
 - \circ $\;$ Any other clinically determined contraindication for PAP treatment $\;$
 - o Patients participating in any type of weight loss treatment program
 - Unstable congestive heart failure or angina pectoris
 - Any other condition to the judgement of the investigator which potentially may jeopardize the completion of the study according to protocol
 - History of alcohol or drug abuse during the last year, substance use disorder at screening

Study Duration:

The study started in December 2023 with the first patient inclusion and active patient assessments (last patient out) is expected in July 2025.

Figure 1: SR 001 Study Flow Chart

PSG=polysomnography, PG=polygraphy, SR=Sleep Revolution diagnostic pathway, PAP=Positive Airway Pressure treatment

Trial Design

The WP8 study is designed as a randomized, controlled, parallel-group, multi- center, multicountry, non-inferiority comparative study.

Randomisation

Eligible patients are allocated in a 1:1 ratio between Standard Care procedures and the Sleep Revolution procedure, using a randomization procedure. The randomization was performed in blocks of 4 patients. The randomization allocates the patients to the first diagnostic procedure which is also the basis of the clinical decision making. However, each patient will also be studied with the respective other diagnostic arm (SC or SR).

The randomization process is described in full within the clinical trial protocol. Details of the randomisation including the final random allocation list is held securely and unavailable to unauthorized trial personnel.

4. Study endpoints and analyses

Primary Endpoint:

• Staff time spent for the sleep apnea diagnostic pathway – comparison between Standard Care (SC) and the Sleep Revolution (SR) model in patients with obstructive sleep apnea (OSA). The detailed staff time protocol is provided in Appendix A.

Secondary analyses:

General descriptive analysis of the patient population

• Description of baseline characteristics of all study participants and the two randomised patient groups (Sleep revolution group and standard care group) according to the following variables: anthropometrics, comorbidities, medications, results from questionnaire data like the degree of daytime sleepiness (ESS score) and additional questionnaire data listed below:

Description of completeness and quality of the technical data collected in the study

- Number of sleep recordings with acceptable quality for the Sleep Revolution study arm at least 1, 2 or all three nights of Self applied Somnography (SAS-PSG),
- Number of sufficient nights in the standard care procedure (SC-PSG)

- Number and proportion of sufficient Withing Watch recordings including physical activity and photoplethysmographic data (pulse, sleep apnea assessment)
- Number of sufficiently answered data in the Sleep Revolution APP with regards to
 - o Sleep diary
 - o Symptom assessment
 - Cognitive test battery
 - Lifestyle information
- Number of sufficiently answered data in the European Sleep Questionnaire data,
- Number of sufficiently answered questionnaires in the Sleep Revolution platform
 - Epworth Sleepiness Scale, Insomnia Severity Index, Fatigue Severity Scale, Pittsburgh Sleep Quality Inventory, Depression Anxiety Stress Scale – short version with 21 questions (DASS21), Clinical Global Impression Scales

Capacity of the novel SR diagnostic pathway to detect clinically significant sleep apnea

Sleep apnea severity and sleep quality

SR procedure: 3 nights: Means, Minimum, and Maximum for: AHI, ODI, T90, Total Sleep Time, % sleep stage distribution, hypoxic burden assessed by ABOSA software

- Standard care procedure: AHI, ODI, T90, Total Sleep Time, % sleep stages, hypoxic burden assessed by ABOSA software
- "First night" and "between night" effects: Differences between nights 1, 2 and 3 in the sleep recording results, in particular night 1 versus 2 or 3. Analysis of variability: %supine position, REM-sleep%, and alcohol intake prior to sleep (dichotomic)
- Frequency of OSA diagnosis in Standard Care versus SR care
- Frequency of no sleep apnea, and "mild to severe" OSA according to the AHI criteria AHI<5, 5-<15, 15-<30 and ≥ 30 events/hour in both arms (SR and SC)
- Frequency of treatment recommendations
- Distribution of recommendation for PAP, OD, surgery, weight reduction, no treatment for the two randomised patient groups: Standard care versus Sleep Revolution based diagnosis
- Frequency of other sleep diagnoses in Standard Care versus SR care
- Frequency of insomnia, combined OSA and insomnia (COMISA), Periodic Limb Movement Disorders (PLMD), Restless Legs Syndrome (RLS)

Prespecified subgroup analyses:

- Sex, even pre-post menopause
- Technical feasibility analysis: Age stratification by tertiles
- Weight change group in the PAP follow-up study

Clinically meaningful outcomes of CPAP treatment in patients with OSA

• Adherence with and efficacy of PAP treatment

Mean values for the treatment period, variability of PAP use over time, residual AHI, leakage.

CPAP-non users: Identification of those patient characteristic: more complex analysis of predictors for PAP non -users by parameters from the diagnostic process (standard care and SR case)

• Effects of PAP treatment

- Change in physiological data like AHI, blood pressure, weight, sleep test data (sleep stages, oxygenation), as well as APP derived cognitive function, and more subjective data like the ESS scores, questionnaires, and the ESQ follow up module; Sleep App parameters: overall wellbeing, treatment rating by the patient, sleep habits (diary), degree of physical activity (subjective ratings). All those data need to be adjusted for PAP adherence.
- Comparison between objective changes by treatment (see point above) with patient reported perception of treatment (data from the questionnaires and APP) through descriptive analysis, correlation analysis and cluster analysis
- Comparison of objective and subjective patient changes with the rating of the sleep doctors in the CGI-change by treatment scale.

Feasibility of the European Sleep Questionnaire (both technical failure and patients ´ inability to perform the SAP)

- Time spent to fill in the questionnaire, even possible or subparts of the questionnaire
- Completeness of data in the ESQ
- Subgroup analysis separated by age and sex
- Patients feedback

Feasibility of the SR digital platform for data transfer

- Percentage missing data, data transfer failure rate, patient experience, health care personnel experience
- Safety and tolerability of self-applied polysomnography
- Patient centred reporting of clinical symptoms in a digital platform

The predictive value of the sleep related novel variables detected by the SR diagnostic pathway (hypoxic burden (ABOSA software), symptom burden (ESQ based data) for three months treatment outcome after CPAP therapy:

- o symptom improvement following therapy: daytime sleepiness and sleep quality
- adherence with PAP treatment (hours used, number of patients with PAP adherence at least 3 or 4 hours, proportion of PAP non acceptance)
- o comparison of outcomes with parameters from standard care

Exploratory Objectives

- Proportion of patients diagnosed with clinically relevant sleep apnea in each arm, proportion of patients with treatment recommendations for CPAP, mandibular advancement devices, or upper airway surgery in each arm of the study.
- Proportion of patients with PAP non-adherence (user time <4h/night) in each study arm
- Sleep apnea alleviation by PAP (calculation of overall efficacy of PAP adjusted for PAP adherence, mean habitual sleep time and residual AHI during PAP use)
- Evaluation of biomarker predictive for hypoxic burden and reduced quality of life (e. g hsCRP, TNF alpha, Hypoxia Inducible Factor), these data are sampled only in few centers as it was not part of the mandatory protocol. Separate analysis in case of sufficient sample size of probes taken.
- Technical failure rate of respective diagnostic pathway
- Association between novel sleep parameters and biomarkers addressed in a subgroup of study centers (metabolic function, inflammation)
- Comparison of sleep test results from Standard Care and Sleep Revolution procedure for each patient where both sleep recording principles were applied (irrespective of randomisation code). Systematic comparison of OSA severity measures and sleep quality.

Safety Endpoints

The following secondary safety assessments are planned according to the schedule of assessments:

- Adverse events (AE), including treatment emergent (TEAE) and serious AEs (SAE)
- Physical examination
- Body weight and BMI
- Vital signs

Table with secondary efficacy endpoints:

Important Secondary Endpoints	Other Secondary Endpoints
Parameters of the SR sleep test analysis:	
 Variables of novel hypoxic markers Variables of respiratory event detection Variables of novel sleep and arousal classification Variables of novel cardiovascular classification (Pulse, ECG, and pulse wave analysis) 	 Number of valid sleep tests in SR and SC diagnostic pathways OSA classification based on three nights of self applied somnography versus classification by standard PG/PSG Sleep apnea diagnosis criteria fulfilled in night 1, 2, or 3 in the SAS somnography
 Parameters of the traditional sleep test analysis – both at baseline and change after 3 months of PAP treatment for Sleep stages and arousal, total sleep time, sleep latencies, total sleep time, sleep efficacy AHI, ODI, Mean and lowest saturation Mean, highest and lowest heart rate 	 Change in sleep quality parameters based on PSG (e.g. total arousal index) from baseline to Week 12 Change in novel objective sleep quality measures (sleep continuum, sleep windows shorter than 30 seconds, other)
 Results from the European Sleep Questionnaire Change in daytime and nocturnal symptoms assessed by the ESQ at baseline and after 12 weeks of CPAP Association ESQ parameters and PSG variables 	 Clinical variables and daytime and nocturnal symptoms associated with response to CPAP treatment Patient/Clinical Global Impression Scale Improvement (PGI-I/ CGI-I): Percentage of patients reported as improved (scores 1 to 3) from baseline to Week 12
 Patient/Clinical Global Impression Scale Severity (PGI-S/CGI-S): Change in mean score from baseline to Week 12 	 Epworth Sleepiness Scale (ESS): Change in mean total score from baseline to Week 12 Insomnia Severity Index (ISI): Change in mean total score from baseline to Week 12
 Pittsburgh Sleep Quality Index (PSQI): Change in mean global score and in mean scores of domains from baseline to Week 1 Association between PSQI measures and sleep test results from SC and SR care Physical activity and mean sleep duration pre and post CPAP 	Association between overnight hypoxic burden (mean of 3 sleep tests) and the change in ESS score after 3 months of CPAP treatment in the SR study arm compared with the association between AHI (single night assessment) and the change in ESS after CPAP treatment in the conventional management arm (both models adjusted for confounders of ESS change

5. Aims and Hypotheses

Aims

- Analyse differences in staff time associated with the SR pathway compared to Standard Care (SC)
- Apply several novel diagnostic parameters and principles which influence the predictive value of the diagnostic method for CPAP treatment efficacy, tolerance and acceptance.
- Assess the technical feasibility of the novel SR diagnostic pathway including selfapplied polysomnography, and the cloud based digital platform for data transfer and data exchange between patients and caregivers.
- Assess the content validity and the predictive capacity for CPAP success of the newly designed European Sleep Questionnaire (ESQ).

Primary Hypothesis:

• The SR procedure provides more reliable and individualized health data during the diagnostic process compared with standard care without an excess of staff time.

List of secondary Hypotheses:

- The ESQ is able to detect treatable traits in sleep apnea patients not yet captured in standard care questionnaires.
- Novel biomarkers from sleep obtained by continuous and automated analysis provide information which better predicts patient outcome
- Self-applied polysomnography is technically feasible but successful application of the technique depends on active patient involvement/participation with acceptable technical failure rates below 10% of sleep tests.
- The first night effect in multiple sleep recordings on sleep apnea metrics is limited and does not systematically differ from the night to night variability between night 2 and 3.
- The outcome of PAP treatment is non-inferior in the SR pathway to SC pathway.
- Additional secondary analyses and hypotheses may be defined including separate protocols and SAP´s. Those will be reviewed and need to be approved by the SR executive committee. More details including an updated SAP will be made available.

6. Sample Size Calculation

Staff time is an important factor for the clinical feasibility of a diagnostic pathway. Today's clinical standard of sleep apnea diagnosis varies considerably between centers and countries in Europe (Fietze 2022). In house polysomnography as well as HSAT are frequently used to establish the final OSA diagnosis and resources in staff-time varies considerable between these two diagnostic methods.

The novel SR pathway aims to provide more diagnostic accuracy by means of three nights of gold standard sleep analysis at patient's home compared to the single-night measures in the sleep laboratory used today. In addition, the SR pathway provides significant enhancement of clinical

phenotyping of patient symptoms, complaints, primary request of help as well as detailed information about relevant aspects of lifestyle and personal habits (physical activity, alcohol consumption, sleep hygiene) and neurocognitive function. The gain of knowledge about the patient ´s disease burden is obvious when using such a comprehensive approach. However, the actual cost in terms of staff time has not yet been evaluated.

All innovation in medicine needs to be justified in terms of cost-benefit. We decided to use stafftime as the primary outcome of the current study. It is estimated that the time of the SR procedure is equal to the time presently used in the SC procedures. Use of the self-applied polysomnography together with machine-learning algorithms of sleep analysis and the digital platform of patient symptom self-reporting will reduce staff time on one hand. On the other hand, user instructions to the patient for the different technologies as well as the evaluation of new information may consume more time compared with the current procedure. We decided to use a non-inferiority study design with 30 minutes as a threshold for equality of staff time within the setting of 24 sleep centers in Europe.

Calculation of the power sample is based on a previous publication (Fischer 2008) and the following assumptions determined from a Delphi round (expert consensus) amongst the participating study centers. More detailed information on staff time for PSG and HSAT currently used at 24 different study sites are not available in the literature. One pilot study for the SR pathway has been performed but no detailed measurement of staff time was performed. However, realistic estimates can be made (see table below).

Work modules	Standard PSG	Standard HSAT	Sleep Revolution	Value
Preparation technical pre/post	15	10	35	
Instructions/Hook up	20-40	5-20	5-30	
Performance of the sleep test	120-480	0 (patient)	0 (patient)	
Evaluation of the sleep test	30-120	5-30	30-90	
Questionnaires	5	5	10	
Additional equipment	0	0	15	
Doctor: interpretation, communication	30-60	15-30	45-60	
Staff time: Estimated range of the mean	220-720	40-95	140-240	
Staff time: Estimated standard deviation of the mean	180	30	60	120

Power calculation:

Significance level (alpha)	1%		
Power (1-beta)	90%	You could say:	
Standard deviation of outcome	120	between the standard and experimental treatment, then 834	
Non-inferiority limit, d	30	sure that the lower limit of a one- sided 99% confidence interval (or equivalently a 98% two-sided	
Sample size required per group	417	confidence interval) will be above the non-inferiority limit of -30.	
Total sample size required	834		
Technical note		Reference	
Calculation based on the formula:		Julious SA. Sample sizes for clinical trials with Normal data. Statis Med. 2004; 23:1921-1986.	
$n = f(\alpha_s \ \beta) \ \times \ 2 \ \times \ \sigma^2 \ / \ d^2$		How to cite this service	
where σ is the standard deviation, and		Sealed Envelope Ltd. 2012. Power calculator for continuous	
$f(\alpha, \beta) = [\Phi^{-1}(\alpha) + \Phi^{-1}(\beta)]^2$		outcome non-inferiority trial. [Online] Available from: https://www.sealedenvelope.com/power/continuous-noninferior/	
• ¹ is the cumulative distribution function of deviate.	a standardised normal	[Accessed Thu Jan 19 2023].	

The power calculation suggests 417 patients in each group, the expected drop-out rate of patients is 20% (results from the SR pilot study, Ferretti et al 2024), resulting in 500 patients per group.

7. Randomization and Blinding

Randomization Method

At screening, the order of diagnostic tests will be randomized. The "randomization system" (RS) will assign an unique identification number to the patient known as the patient number. This number will be associated with the patient throughout the study. Each patient signing an informed consent form (ICF) must be entered into the RS regardless of eligibility to obtain a patient number. This 8-digit number will consist of a 3-digit country specific code, followed by a 2-digit site identification and a 3-digit number assigned sequentially within each site to each patient, starting at 001.

At the randomization visit, all eligible patients will be randomly assigned in a 1:1 ratio to follow the routine clinical management or to be part of the SR clinical pathway. Centres using polysomnography as routine sleep evaluation procedure are asked to use this method in all of the study patients at this centre, and vice versa for those centers using cardiorespiratory polygraphy as the routine method. By this procedure, the study aims to recruit at least 40% of patients in the traditional clinical routine to be assessed by PSG. No formal stratification for anthropometric factors like age, BMI, gender or comorbidities will be performed.

Patients will be assigned a randomization number through the RS. Once a randomization number is allocated to one patient, it may not be assigned to another patient even if the former discontinued the study. The randomisation list is exemplified in appendix B.

Blinding

This is an open label, randomized, cross over study. Blinding of the clinical pathway is not possible for either the patient or the caregiver. However, results of the second diagnostic package (SR or SC) will be blinded at the timepoint for the final diagnosis and treatment recommendation at the end of the diagnostic process (see decision point in figure 1).

The PAP treatment phase and the follow-up are similar in the two groups.

8. Statistical Methods

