The statistical programs SPSS and the R software package R version 4.3.1, located in a data cluster at Reykjavik University, Iceland, are available. All analysis will be performed by authorized personnel on this cluster.

• Data Management Software: REDCap and Excel are used for data management.

13. Reporting and Interpretation of Results

• Presentation of Results:

Results will be clearly presented using tables, figures, and confidence intervals: **Tables** will summarize descriptive statistics, model estimates, and p-values. **Figures** (e.g., bar charts, box plots, scatter plots) will illustrate data distributions, group comparisons, and model diagnostics.

Confidence Intervals (95%) will accompany key estimates to indicate precision. **Text** will highlight main findings, including any deviations or unexpected results. These methods will ensure clarity and support interpretation of the study's outcomes.

• Interpretation of Results:

Significant findings (p < 0.05) will be interpreted as evidence of an association or effect, while non-significant findings will not be taken as proof of no effect but rather as inconclusive. Effect sizes and confidence intervals will be emphasized to assess clinical relevance, regardless of statistical significance.

• Potential limitations of the Analysis:

This is a pan European study including patients from 24 sleep centers in 15 countries. New technology will be applied to all patients and health care professionals. The following limitations of the analysis may occur:

- Heterogeneity Across Centers: Differences in referral patterns, clinical routines, experience with remote technology, and treatment traditions across the 24 centers in 15 countries may introduce variability that is not fully accounted for, potentially affecting the comparability of patient populations and treatment effects.
- **Health System Variability**: Diverse healthcare infrastructures and access to care may influence treatment delivery, follow-up, and adherence, impacting outcome measures.
- Cultural and Societal Influences: Variations in cultural attitudes toward symptoms, treatment expectations, and doctor-patient interactions may affect both patient-reported outcomes and clinician assessments.
- **Baseline Differences**: Systematic differences in symptom burden and patient expectations at baseline between countries or centers may confound treatment effects, even after statistical adjustment.

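### The secondary hypothesis that PAP outcome is non-inferior in the SR pathway has no endpoint, margin, confidence level or population, and the data that could address it come only from PAP starters selected after randomisation

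*SAP*

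**What the plan says.** Section 5, in the list of secondary hypotheses, states: "The outcome of PAP treatment is non-inferior in the SR pathway to SC pathway". It says no more about how this would be judged.

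Section 3 describes how patients reach the treatment phase. Under Randomisation: "The randomization allocates the patients to the first diagnostic procedure which is also the basis of the clinical decision making". Under Study Design, on the 3-month part: "Only patients initiating therapy with PAP will be approached for participation in the subsequent part of the study".

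Section 4 lists many PAP outcomes under "Adherence with and efficacy of PAP treatment" and under effects of treatment (AHI, blood pressure, ESS, questionnaires, app data and others). Of the treatment effects it says: "All those data need to be adjusted for PAP adherence". It also plans to report "Distribution of recommendation for PAP, OD, surgery, weight reduction, no treatment for the two randomised patient groups", and among the exploratory objectives the proportion non-adherent (below 4 h/night) in each study arm.

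On populations, Section 8.1 places secondary outcomes in the per-protocol cohort, which Section 8.3 defines as patients completing the diagnostic pathway. Section 8.5, Example 1, which concerns ESS change after CPAP, names the ITT population instead. Section 13 says that "non-significant findings will not be taken as proof of no effect but rather as inconclusive".

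**The concern.** A non-inferiority claim needs a named endpoint, a margin, a confidence level and groups that differ only by allocation. The SAP supplies none of the first three for PAP outcome, and its design does not supply the fourth.

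The pathways may send different numbers or kinds of patients to PAP; the SAP itself compares diagnoses and recommendations between them. A pathway that starts fewer and more severe patients could show better outcomes among its starters without being a better strategy. A pathway that starts more and milder patients could look worse without being worse. The trial could then report on PAP outcome in a way that reflects who was selected rather than what the pathway achieved.

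**Working it through.** **1. The SAP's only non-inferiority calculation (Section 6).** Inputs: margin 30 min, SD 120 min, one-sided alpha 1%, power 90%, true difference 0.

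n per group = (2.326 + 1.282)² × 2 × 120² / 30² = 13.02 × 32 = 416.5, so 417 per group and 834 in total. This reproduces the stated figures. It concerns staff time and gives no margin or power for PAP outcome.

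**2. Who can be compared.**
- Randomisation assigns the first pathway (Section 3).
- That pathway is the basis of the diagnosis and treatment decision (Section 3).
- Only patients who start PAP are approached for the 3-month part (Section 3).
- So 3-month PAP data exist only in a subset defined after randomisation and partly by the randomised pathway.

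Neither population label changes this. Completing the diagnostic pathway does not make a patient a PAP starter, and calling the set ITT does not create treatment data for patients who never started. Adjusting for PAP adherence conditions on a further variable measured after randomisation.

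**3. What margin the numbers could support (illustration).** The share starting PAP is not in the SAP, so it is assumed. With m starters per arm out of 500, 90% power, one-sided 2.5% and true difference 0, the smallest supportable margin in SD units is (1.960 + 1.282) × √(2/m):

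| Assumed share starting | m | Margin at 2.5% | Margin at 1% |
|---|---|---|---|
| 30% | 150 | 0.37 SD | 0.42 SD |
| 50% | 250 | 0.29 SD | 0.32 SD |
| 70% | 350 | 0.25 SD | 0.27 SD |
| 90% | 450 | 0.22 SD | 0.24 SD |

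**4. What selection alone could do (simulation, all inputs assumed).** Severity is standard normal. PAP starts when severity plus measurement error (SD 0.8) exceeds a cut-off. Benefit has SD 1 and rises with severity at a slope of 0.1 to 0.5. In SC 60% start. There is no true pathway effect. The SR minus SC difference in mean benefit among starters is:
- SR starts 50%: +0.01 to +0.06 SD
- SR starts 70%: -0.01 to -0.06 SD
- SR starts 80%: -0.02 to -0.11 SD
- SR starts 60% with a less noisy measure (error SD 0.45): +0.01 to +0.04 SD

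For scale, take the most extreme case, with 300 SC and 400 SR starters out of 500 each. The smallest supportable margin at one-sided 2.5% and 90% power is 3.242 × √(1/300 + 1/400) = 0.248 SD. A shift of 0.114 SD would use 0.114/0.248 = 46% of it.

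**5. Why the denominator matters (one assumed case).** Of 500 per arm, SR starts 200 with 140 adherent and SC starts 260 with 156 adherent. Among starters: 140/200 = 70% against 156/260 = 60%, so SR is 10 points higher. Among all randomised: 140/500 = 28.0% against 156/500 = 31.2%, so SR is 3.2 points lower. Exchanging the arm labels gives the opposite picture. The case shows that the sign can depend on the denominator; it does not predict the result.

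**The case against.** **Starters are not named as the denominator.** A reader might infer that the SAP plans a biased denominator. It does not say so: no sentence assigns PAP starters to this hypothesis, Section 8.1 points to the per-protocol cohort and Example 1 to ITT. This stands as a limit on wording. The restriction to starters is an inference from who is followed up, but no other patients have 3-month PAP data.

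**Section 13 protects against a false claim.** A reader might infer that its rule on non-significant results would lead to a wrong non-inferiority conclusion. The opposite is true: the rule blocks that step, and Section 13 asks for effect sizes and confidence intervals. This objection stands. It also means the SAP gives no route by which the stated hypothesis could be supported.

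**The detail is deferred.** Section 8.5 says that describing every secondary analysis is not feasible, Section 5 foresees further SAPs, and the protocol is not at hand. A margin may therefore exist or follow. This stands for the missing margin but not for the selection, which no margin removes.

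**Differential selection would be visible.** Recommendations by randomised group, non-adherence by arm and the within-patient comparison of both recordings are already planned. This stands in part: these outputs would show a difference in selection, but they do not restore a randomised comparison, and the non-adherence proportion has no stated denominator.

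**Counting every non-starter as a failure would be wrong too.** It would score patients without OSA, or with another recommended treatment, as PAP failures and would reward the pathway that prescribes more PAP. This stands and shapes the fix.

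**Conclusion.** The point holds for this one secondary hypothesis; the primary staff-time comparison is untouched. As written, the SAP cannot support a conclusion that PAP outcome is non-inferior in SR. The claim has no endpoint, margin, confidence level or population, and the follow-up data come from groups formed after randomisation.

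A reader might go further and conclude that the comparison will favour SR, or that the bias is large. The SAP supports neither. It gives no PAP-start rates, outcome SD or severity-benefit relation, so size and direction are unknown. In the assumed scenarios the shift is modest (-0.11 to +0.06 SD) and goes both ways. The statement in Section 7 that the PAP phase is similar in the two groups concerns what happens in that phase, not who enters it.

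**What to change.** In Section 5, withdraw the non-inferiority wording for PAP outcome. In Section 8.5, state the following:

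- The SR minus SC difference in PAP outcome among PAP starters is reported with its 95% CI, labelled descriptive and not a randomised comparison.
- Baseline severity of the starters, from both recordings, is shown by arm.
- This between-arm contrast is not adjusted for PAP adherence.
- Beside it, with all randomised patients as denominator, each arm's proportions recommended PAP, starting PAP, and using PAP at least 4 h/night at 3 months (the SAP's own threshold) are given. Starters without follow-up are shown separately.
- The all-randomised proportion also reflects how many patients each pathway sends to PAP, so a lower value is not in itself a worse outcome.

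If a non-inferiority claim is to be kept, fix one endpoint defined for every randomised patient, a justified margin and a confidence level before database lock.

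The cost is SAP wording and a few table rows, with no new assessments. Hours of use may be missing for starters who decline the follow-up part, hence their separate line. The SAP was signed in May and June 2025 with the last patient expected out in July 2025, so the change should be made promptly.
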